ANNEX 1. Clavien-Dindo Classification

(GRAVITY - POSTOPERATIVE COMPLICATION)

- I. Any deviation from the normal postoperative period that does not require surgical or endoscopic reintervention. Includes additional use of electrolyte solutions, antiemetics, antipyretics, analgesics, and physical therapies. Includes superficial infection
- II. Pharmacological treatment different from the previous ones. Blood transfusions or blood products and parenteral nutrition
- III. Requires surgical, endoscopic or radiological reintervention:
 - a. Without general anesthesia
 - b. With general anesthesia
- IV. Complications that threaten the life of the patient and require treatment in intermediate or intensive care:
 - a. Organ dysfunction (includes hemodialysis)
 - b. Multiple organ dysfunction
- V. Death of the patient

**ANNEX 2. CLASSIFICATION AMERICAN SOCIETY OF ANESTHESIOLOGIST
(ASA)**

I: No systemic disease.

II: Mild systemic disease.

III: Systemic disease that affects the activity of the patient.

IV: Serious disease, but not dying patient.

V: Dying patient, unexpected survival.

***Saklad M. Grading of patients for surgical procedures. Anesthesiology 1941;
2:281–4. Dripps RD. New classification of physical status. Anesthesiology 1963;
24:111.***

ANNEX 5. QUESTIONNAIRE SF-36

SF-36 QUESTIONNAIRE

Name: _____ Ref. Dr: _____ Date: _____
ID#: _____ Age: _____ Gender: M / F

Please answer the 36 questions of the Health Survey completely, honestly, and without interruptions.

GENERAL HEALTH:

In general, would you say your health is:

- Excellent Very Good Good Fair Poor

Compared to one year ago, how would you rate your health in general now?

- Much better now than one year ago
 Somewhat better now than one year ago
 About the same
 Somewhat worse now than one year ago
 Much worse than one year ago

LIMITATIONS OF ACTIVITIES:

The following items are about activities you might do during a typical day. Does your health now limit you in these activities? If so, how much?

Vigorous activities, such as running, lifting heavy objects, participating in strenuous sports.

- Yes, Limited a lot Yes, Limited a Little No, Not Limited at all

Moderate activities, such as moving a table, pushing a vacuum cleaner, bowling, or playing golf

- Yes, Limited a Lot Yes, Limited a Little No, Not Limited at all

Lifting or carrying groceries

- Yes, Limited a Lot Yes, Limited a Little No, Not Limited at all

Climbing several flights of stairs

- Yes, Limited a Lot Yes, Limited a Little No, Not Limited at all

Climbing one flight of stairs

- Yes, Limited a Lot Yes, Limited a Little No, Not Limited at all

Bending, kneeling, or stooping

- Yes, Limited a Lot Yes, Limited a Little No, Not Limited at all

Walking more than a mile

- Yes, Limited a Lot Yes, Limited a Little No, Not Limited at all

Walking several blocks

- Yes, Limited a Lot Yes, Limited a Little No, Not Limited at all

Walking one block

- Yes, Limited a Lot Yes, Limited a Little No, Not Limited at all

Bathing or dressing yourself

Yes, Limited a Lot Yes, Limited a Little No, Not Limited at all

PHYSICAL HEALTH PROBLEMS:

During the past 4 weeks, have you had any of the following problems with your work or other regular daily activities as a result of your physical health?

Cut down the amount of time you spent on work or other activities

Yes No

Accomplished less than you would like

Yes No

Were limited in the kind of work or other activities

Yes No

Had difficulty performing the work or other activities (for example, it took extra effort)

Yes No

EMOTIONAL HEALTH PROBLEMS:

During the past 4 weeks, have you had any of the following problems with your work or other regular daily activities as a result of any emotional problems (such as feeling depressed or anxious)?

Cut down the amount of time you spent on work or other activities

Yes No

Accomplished less than you would like

Yes No

Didn't do work or other activities as carefully as usual

Yes No

SOCIAL ACTIVITIES:

Emotional problems interfered with your normal social activities with family, friends, neighbors, or groups?

Not at all Slightly Moderately Severe Very Severe

PAIN:

How much bodily pain have you had during the past 4 weeks?

None Very Mild Mild Moderate Severe Very Severe

During the past 4 weeks, how much did pain interfere with your normal work (including both work outside the home and housework)?

Not at all A little bit Moderately Quite a bit Extremely

ENERGY AND EMOTIONS:

These questions are about how you feel and how things have been with you during the last 4 weeks. For each question, please give the answer that comes closest to the way you have been feeling.

Did you feel full of pep?

- All of the time
- Most of the time
- A good Bit of the Time
- Some of the time
- A little bit of the time
- None of the Time

Have you been a very nervous person?

- All of the time
- Most of the time
- A good Bit of the Time
- Some of the time
- A little bit of the time
- None of the Time

Have you felt so down in the dumps that nothing could cheer you up?

- All of the time
- Most of the time
- A good Bit of the Time
- Some of the time
- A little bit of the time
- None of the Time

Have you felt calm and peaceful?

- All of the time
- Most of the time
- A good Bit of the Time
- Some of the time
- A little bit of the time
- None of the Time

Did you have a lot of energy?

- All of the time
- Most of the time
- A good Bit of the Time
- Some of the time
- A little bit of the time
- None of the Time

Have you felt downhearted and blue?

- All of the time
- Most of the time
- A good Bit of the Time
- Some of the time
- A little bit of the time
- None of the Time

Did you feel worn out?

- All of the time
- Most of the time
- A good Bit of the Time
- Some of the time
- A little bit of the time
- None of the Time

Have you been a happy person?

- All of the time
- Most of the time
- A good Bit of the Time
- Some of the time
- A little bit of the time
- None of the Time

Did you feel tired?

- All of the time
- Most of the time
- A good Bit of the Time
- Some of the time
- A little bit of the time
- None of the Time

SOCIAL ACTIVITIES:

During the past 4 weeks, how much of the time has your physical health or emotional problems interfered with your social activities (like visiting with friends, relatives, etc.)?

- All of the time
- Most of the time
- Some of the time
- A little bit of the time
- None of the Time

GENERAL HEALTH:

How true or false is each of the following statements for you?

I seem to get sick a little easier than other people

Definitely true Mostly true Don't know Mostly false Definitely false

I am as healthy as anybody I know

Definitely true Mostly true Don't know Mostly false Definitely false

I expect my health to get worse

Definitely true Mostly true Don't know Mostly false Definitely false

My health is excellent

Definitely true Mostly true Don't know Mostly false Definitely false

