 - To evaluate the possible improvement in the quality of life of the transplanted patient derived from the absence of postsurgical drainage (SF-36).
 - Evaluate the postoperative stay in both groups.

- **STUDY DESIGN**

Unmasked European multicenter randomized clinical trial with two arms parallel to the study.

Patients who meet the inclusion criteria will be offered to participate in this study by signing an informed consent. An informed consent approved by the Research Ethics Committee of the Virgen de la Arrixaca University Hospital will be used.

Patients who give their consent for the study will be randomized to the drainage group (D) and the control group without drainage (ND) before the beginning of the abdominal wall closure.

In the drainage group (D), it will be placed on the right flank / right iliac fossa. The drain will be connected to a bag and fixed to the skin with a silk. Said drain will be placed at the level of the surgical bed.

Regarding the control group, intraoperative drainage will not be placed, except when the surgeon's discretion considers it necessary due to the high risk of bleeding, bile leakage or any other process / complication in which it may benefit from intra-abdominal drainage.

All patients, regardless of the randomization group, will receive a quality of life questionnaire (SF-36) prior to surgery that they must complete.

All patients will receive routine antibiotic prophylaxis 60 minutes before surgery, repeating the number of doses that are required according to blood loss and surgical time. Antibiotic prophylaxis will be adjusted according to the resistance protocols of each participating center.

○ **DATA COLLECT**

The following variables will be collected for each patient:

- **Recipient preoperative** variables: gender, age, pre-transplant stay, BMI, ASA, diabetes, HTN, dialysis, MELD, Child-Pugh, serology, albumin, bilirubin, INR, CRP, creatinine, ascites, SBP, prothrombin time, encephalopathy, time from SSI to HT (months), retransplantation, previous surgeries, cirrhosis etiology, indication for transplantation, sarcopenia.
- **Donor** characteristic variables: age, stay in ICU, vasoactive drugs, cultures, antibiotics, CIT, WIT, type of donation (DBD / DCD), previous immunosuppression.

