- **Intraoperative** variables: placement or not of abdominal drainage, surgical time (min), transfusions, blood loss, surgical technique, arterial anastomosis type, biliary anastomosis type, donation with extended criteria, recipient with extended criteria, clamping times.
- **Postoperative** variables: ICU stay, hospital stay, abdominal complications (collection, bile leak, hematoma, hemorrhage, paralytic ileus, ascites, bleeding, wound drainage complications, vascular anastomosis complications, mechanical

obstruction, hollow viscus perforations, wound complications surgery), graft function, post-transplant antibiotic therapy, post-transplant immunosuppressive regimen, number of post-HT HC, mortality at 90 days, global complications at 90 days.

○ **FOLLOW-UP**

The drain output will be evaluated daily after the surgical procedure. The quantity will be measured in milliliters and the appearance of the drainage will be categorized as serous, hematic, biliary or purulent. Its removal will be assessed on the 3rd postoperative day unless the patient shows signs of bleeding, bile leakage, intra-abdominal infection or any other complication that contraindicates its removal. When any of these complications that have delayed removal of the intra-abdominal drain are resolved, the drain should be removed.

Patients will be followed up during the postoperative period on a daily basis and complications will be observed at 90 days from discharge.

Calls will be made from discharge, the first 30 days every 15 days, from the month of discharge the periodicity will be monthly until 90 days from the intervention. The last follow-up call will be made on day 90. Subsequently, the follow-up protocol of each center will be followed.

The SF-36 quality of life questionnaire will be performed preoperatively, at one month and at 4 months after surgery.

○ **Sampling methods and assignment of subjects to groups. Randomization.**

Subjects will be recruited at the pre-liver transplant consultation and/or at the time of inclusion on the transplant waiting list (Liver Transplant Committee - General Surgery Sessions Room - 3rd Floor Hospital Clínico Universitario Virgen de la Arrixaca, Murcia - Tuesday at 12h) among those patients who meet the criteria for participation in the study.

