- **SF-36:** Physical function, physical role, body pain, general health, vitality, social function, emotional role, mental health (on inclusion in the waiting list, one month after surgery, 4 months after surgery).

- **SUBJECT FOLLOW-UP**

As we have previously indicated, patients will be evaluated daily by the research staff during their hospital stay. Those who were discharged before day 30 post-transplant will continue to contact the researchers by phone and report any event related to the insertion point of the drain.

Calls will be made from discharge, the first 30 days every 15 days, from the month of discharge the periodicity will be monthly until 90 days from the intervention. The last follow-up call will be made on day 90.

- **SAFETY ASSESSMENT (only for medicines, food or other therapeutic procedures).**

All patients assigned to the control group (DN) will be reevaluated intraoperatively. If, for obvious clinical reasons, the placement of the drain is required, said patient will be excluded from the study (randomization will not be carried out, so it would not be included in the RCT) and the drain will be placed.

Patient safety was not impaired at any point in the study, with the intervention group (D) being the routine procedure in LT and the control group (ND) re-evaluated intraoperatively.

- **STATISTICS**

- **Data handling**

The data collection will be carried out through a Data Collection Notebook, capturing all the data in it legibly and in blue pen. Subsequently, said data will be dumped into a CRD through a spreadsheet. This sheet allows online access for the different study participants, to perform randomization and assign the patient code and to enter the data of each of the included patients. Patients will be included without personal data or identification documents, only an identification code that will be assigned to each one at the time of randomization. Once the trial is finished, all the data collected in the database will be evaluated for the writing of the final report.

All the documentation related to the study will remain stored in the Investigator's File, in the participating center, under the custody of the Principal Investigator until the end of the study. Once the study is finished, the documentation will be indexed and transferred to the general file of the center, complying with the recommendations established with respect to the Good Clinical Practice Standards.

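### In Annex 5 the first SF-36 social item names only emotional problems and gives no recall period, so it does not match its partner and weakens the social-function domain

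*Combined protocol and SAP*

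**What the plan says.** The first of the two secondary objectives is a possible gain in quality of life from leaving the drain out, measured with the SF-36. Study Variables lists the domains as "Physical function, physical role, body pain, general health, vitality, social function, emotional role, mental health". On timing, Follow-up says: "The SF-36 quality of life questionnaire will be performed preoperatively, at one month and at 4 months after surgery".

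The questionnaire is in Annex 5, where two items stand under a Social activities heading:

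- **First item:** "Emotional problems interfered with your normal social activities with family, friends, neighbors, or groups", with the answers "Not at all Slightly Moderately Severe Very Severe".
- **Second item:** "During the past 4 weeks, how much of the time has your physical health or emotional problems interfered with your social activities", with five answers graded by frequency.

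The plan gives no SF-36 scoring rule and no map from items to domains. Secondary Variables Analysis says only that all included variables will be studied by univariate and multivariate methods.

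**The concern.** The intervention is a physical device. The protocol's case for omitting it rests partly on physical grounds: the Justification cites pain and infection at the insertion point, and Sample Size cites relief from discomfort. Patients whose social life was limited by pain or poor mobility, but who were not distressed, could reasonably answer the first item with its lowest category. They could report the limitation only on the second item.

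The missing recall period is a separate problem. At the one-month visit the second item confines recall to roughly the time since surgery. The first sets no limit, so some patients may include their illness before transplant. The two answers would then describe different periods as well as different causes.

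At stake is the meaning of one listed domain. A null result on social function could reflect no effect, or an item that did not ask about the relevant cause. Analysis cannot recover an answer to a question that was not put.

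**Working it through.** The plan states no figure on this point, so there is nothing to reproduce. The check compares wording, with one short piece of arithmetic.

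**1. The two items side by side (Annex 5).**

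| Feature | First social item | Second social item |
|---|---|---|
| Cause named | Emotional problems only | Physical health or emotional problems |
| Recall period | None | Four weeks |
| Stem | None; a statement with a question mark | Asks how much of the time |
| Answers | Five; the first three grade amount, the last two are severity labels | Five, all graded by frequency |

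**2. Could the first item inherit a recall period?** The block before it, on emotional health problems, has a four-week stem, but that stem introduces items on work and daily activities. The social item starts a new section under its own heading. The pain items and the energy block that follow each state their own four-week window.

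Lacking a four-week window is not unique to this item. The ten activity items ask about the present, and the general-health items are present-tense or compare with a year ago. What sets this item apart is that it is worded in the past tense with no reference period at all.

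**3. Is an item missing?** Count by block: general health 2, activities 10, physical role 4, emotional role 3, first social 1, pain 2, energy and emotions 9, second social 1, general-health statements 4. The sum 2 + 10 + 4 + 3 + 1 + 2 + 9 + 1 + 4 = 36 matches the number the annex announces. Exactly two items are social, and one of them is affected.

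**4. Range of dilution.** Assumptions, none of them in the documents: the domain is the equally weighted mean of these two items on a common scale; the drain's effect acts through physical health; it would shift both items by *d* if both asked about physical health; and the domain SD is unchanged. Let *f* be the share of *d* that the first item still picks up, for example through distress caused by pain. Then

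domain effect = (*d* + *f·d*)/2 = *d*(1 + *f*)/2.

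| *f* | Domain effect | Dilution |
|---|---|---|
| 1 | 1.000 *d* | none |
| 0.75 | 0.875 *d* | 12.5% |
| 0.50 | 0.750 *d* | 25% |
| 0.25 | 0.625 *d* | 37.5% |
| 0 | 0.500 *d* | 50% |

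The documents give no value for *f*, so only the range from nothing to one half can be stated.

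**The case against.** **The annex may not be the form in use.** The trial is described as European and multicentre, recruitment is described at a Spanish hospital, and the annex is in English. Patients may complete another language version without this wording. A line could also have been lost when the annex was converted to text. That is unlikely, since the item begins with a capital letter under its own heading and has its own answers, but it cannot be excluded. This objection stands, and it is why the fix begins with a check.

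**The consequence is limited.** This is one item of 36, in one of eight domains, for a secondary objective. The ten activity, four physical-role and two pain items (10 + 4 + 2 = 16) cover physical effects directly. Both arms get the same form. The overlap with routine drainage is also short: "Its removal will be assessed on the 3rd postoperative day unless the patient shows signs of bleeding", while the first postoperative SF-36 is at one month. All of this stands and limits the point's weight, but it does not make the item sound.

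**A stronger reading is tempting.** A reader might infer that half the domain cannot register a physical effect and that power collapses. With 174 per arm and a two-sided 5% test, 0.30 SD gives 0.30 × √87 = 2.80 and about 80% power; 0.15 SD gives 0.15 × √87 = 1.40 and about 29%. The arithmetic is right, but the documents do not support the claim. They give no weighting, no SD and no expected SF-36 effect. The lower figure also needs *f* = 0, although physical trouble can register through distress, and a complete questionnaire from all 174 patients in each arm.

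**Conclusion.** The point holds as a defect in one item of the instrument, visible from Annex 5 alone. The first social item differs from its partner in cause, recall period and stem, and its last two answers do not fit the question. If Annex 5 is what patients complete, social function will be less sensitive to physical effects of the drain and harder to interpret.

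A purely physical effect on the domain would be diluted by between nothing and one half, assuming equal weighting and an unchanged SD. No power figure follows from the documents. Nor does any inference that the comparison between arms is biased, that the primary endpoint is touched, or that the domain is lost: the second item still carries usable information. The correction is worth making because it is small and has to be made before the data are collected.

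**What to change.** 1. Check Annex 5 against the SF-36 form that patients actually receive, in each language used.
2. If the wording is the same, amend the first social item so that it asks about physical health or emotional problems over the same four-week window as the second item, with a stem asking how much. Replace its answers with an extent-type set; the annex already has one, for the item on pain interfering with work. Using the validated form in each centre's language achieves the same result.
3. Flag any forms already completed with the old wording. For those patients, analyse social function from the second item alone at every visit, because scores from old and new wording are not directly comparable within a patient. Alternatively, report the second item alone as a sensitivity analysis in all patients.

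The cost is one line of the questionnaire, changed by amendment. The downside is the flagging in step 3 and, for the patients concerned, a one-item score in place of a two-item score.
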